2.1.2 Inclusion Criteria - Phase II SCLC

2.1.2.1 Age ≥ 18 years.

2.1.2.2 Patients must have histologically or cytologically confirmed diagnosis of SCLC from a CLIA-certified laboratory.

2.1.2.3 Have received and progressed during or after a platinum-based standard chemotherapy regimen and/or an immune-checkpoint inhibitor

2.1.2.4 Patients could have received any number of therapies for relapsed or progressive disease, including re-treatment with original frontline regimen. A minimum of 2 weeks will be required from any prior therapy, including chemotherapy, immunotherapy and/or radiation. In addition, recovery to Grade ≤ 1 from all reversible toxicities related to prior therapy is required at study entry. No previous irradiation to the site of measurable or evaluable disease, unless that site had subsequent evidence of progression.

2.1.2.5 Patients must have measurable disease as per Response Evaluation Criteria in Solid Tumors, version (RECIST 1.1). See Section 6.3 for the evaluation of measurable disease.

2.1.2.6 Radiographic evidence of disease progression after initial therapy should have been documented.

2.1.2.7 ECOG performance status ≤ 2 (see [Appendix A](#), Section 16.1).

2.1.2.8 Patients with treated brain metastases (surgery, whole or stereotactic brain radiation) are allowed provided the lesions have been stable for at least 2 weeks and the patient is off steroids or is on a stable dose of steroids. Patients with brain metastases should not require use of enzyme-inducing antiepileptic drugs (e.g., carbamazepine, phenytoin, or phenobarbital) within 14 days before first dose and during study. Use of newer antiepileptics that do not produce enzyme induction drug-drug interactions (DDIs) is allowed.

2.1.2.9 Patients must have normal organ and marrow function as defined below:

- leukocytes	$\geq 3,000/\text{mcL}$
- absolute neutrophil count	$\geq 1,500/\text{mcL}$ without growth factor support
- platelets	$\geq 100,000/\text{mcL}$ without growth factor support
- hemoglobin	$\geq 9 \text{ g/dL}$, and no blood transfusion within 4 weeks.

OR

- hemoglobin	$>10 \text{ g/dL}$, and no blood transfusion within 2 weeks.
--------------	---

- total bilirubin	$\leq 1.5 \times$ ULN (unless Gilbert's Disease)
- AST(SGOT)/ALT(SGPT)	$\leq 2.5 \times$ institutional upper limit of normal ($\leq 5 \times$ ULN if liver mets)
- creatinine	\leq ULN
OR	

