- creatinine clearance	≥ 51 mL/min (calculated using the Cockcroft-Gault formula) for patients with creatinine levels above institutional normal.

2.1.2.10 Individuals who can father children and their partners must agree to use highly effective contraception (refer to section 4.2 for details) prior to study entry, for the duration of study participation and for 3 months following last dose of study drugs. Individuals who are of childbearing potential and sexually active must agree to the use of 1 highly effective form of contraception, and their partners, if they can father children, must use a condom, or they must totally/truly abstain from any form of sexual intercourse, throughout their participation in the study and for at least 6 months after last dose of study drugs. Individuals should not donate sperm throughout the period of taking olaparib and for 3 months following the last dose of olaparib. Individuals of childbearing potential (IOCBP) are defined as being physically capable of becoming pregnant unless unable to have children because of surgery or other medical reasons (effective tubal ligation, ovaries or the uterus removed, or are post-menopausal). Post-menopausal is defined as:

- Amenorrheic for 1 year (12 months in a row) or more following cessation of exogenous hormonal treatments,
- LH and FSH levels in the post-menopausal range for individuals under 50,
- radiation-induced oophorectomy with last menses >1 year ago,
- chemotherapy-induced menopause with >1 year interval since last menses,
- or surgical sterilization of participant (bilateral oophorectomy or hysterectomy) and/or partner.

2.1.3 Inclusion Criteria for Urothelial Carcinoma Expansion Cohort (accrual to the cohort ended with amendment version 08/17/2022)

2.1.3.1 Patients must have a histologically confirmed diagnosis of urothelial carcinoma of the bladder, urethra, ureter, or renal pelvis from a CLIA-certified laboratory, with measurable disease by RECIST (version 1.1) including lymphadenopathy and visceral metastatic disease

2.1.3.2 Adult patients ≥ 18 years of age.

2.1.3.3 Patient must have received at least one platinum based regimen of chemotherapy and/or an immune-checkpoint inhibitor if appropriate with progressive disease.

2.1.3.4 Prior antiangiogenic and radiation therapy are permitted (2-week washout from therapy is required).

2.1.3.5 Bisphosphonates and denosumab are permitted if on a stable dose for ≥ 4 weeks.

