2.3.2 Screening activities performed after a consent for screening has been signed

The following activities will be performed only after the participant has signed the study consent OR the consent for study 01-C-0129 (provided the procedure is permitted on that study) on which screening activities may also be performed. Assessments performed at outside facilities or on another NIH protocol within the timeframes below may also be used to determine eligibility once a participant has signed the consent.

Screening must be completed within 2 weeks prior to C1D1.

- History and physical exam (including height, weight, vital signs and performance status)
- Blood tests (for organ function)
 - Complete blood count (CBC/Diff)
 - Acute care panel (sodium, potassium, chloride, total CO₂ (Bicarbonate), creatinine, glucose, urea nitrogen)
 - Hepatic panel (alkaline phosphatase, ALT/GPT, AST/GOT, total bilirubin, direct bilirubin)
 - Prothrombin time (PT)
 - Partial thromboplastin time (PTT)
 - Viral Markers Protocol Screen (HBsAg, anti-HCV, anti-HIV) within 3 months of C1D1.
- Collection of pathology reports from any certified laboratory for confirmation of diagnosis (may be done prior to the two week screening window).
- CT chest/abdomen/pelvis (mCRPC patients will have baseline CT scans and technetium-99 bone scan imaging within 30 days prior to initiation of therapy)
- Electrocardiogram
- Echocardiogram within 4 weeks prior to C1D1
- Urine or serum HCG for IOCBP (to be performed within 3 days prior to C1D1)
- Serum testosterone level (mCRPC patients only)

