6.3.2 Disease Parameters

Measurable disease: Measurable lesions are defined as those that can be accurately measured in at least one dimension (longest diameter to be recorded) as:

- By chest x-ray: ≥ 20 mm;
- By CT scan:
 - Scan slice thickness 5 mm or under as ≥ 10 mm with CT scan

- Scan slice thickness >5 mm: double the slice thickness
- With calipers on clinical exam: ≥ 10 mm.

All tumor measurements must be recorded in millimeters (or decimal fractions of centimeters).

Malignant lymph nodes. To be considered pathologically enlarged and measurable, a lymph node must be ≥ 15 mm in short axis when assessed by CT scan (CT scan slice thickness recommended to be no greater than 5 mm). At baseline and in follow-up, only the short axis will be measured and followed.

Non-measurable disease. All other lesions (or sites of disease), including small lesions (longest diameter <10 mm or pathological lymph nodes with ≥ 10 to <15 mm short axis), are considered non-measurable disease. Bone lesions, leptomeningeal disease, ascites, pleural/pericardial effusions, lymphangitis cutis/pulmonitis, inflammatory breast disease, and abdominal masses (not followed by CT or MRI), are considered as non-measurable.

Note: Cystic lesions that meet the criteria for radiographically defined simple cysts should not be considered as malignant lesions (neither measurable nor non-measurable) since they are, by definition, simple cysts.

‘Cystic lesions’ thought to represent cystic metastases can be considered as measurable lesions, if they meet the definition of measurability described above. However, if non-cystic lesions are present in the same patient, these are preferred for selection as target lesions.

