Target lesions. All measurable lesions up to a maximum of 2 lesions per organ and 5 lesions in total, representative of all involved organs, should be identified as **target lesions** and recorded and measured at baseline. Target lesions should be selected on the basis of their size (lesions with the longest diameter), be representative of all involved organs, but in addition should be those that lend themselves to reproducible repeated measurements. It may be the case that, on occasion, the largest lesion does not lend itself to reproducible measurement in which circumstance the next largest lesion which can be measured reproducibly should be selected. A sum of the diameters (longest for non-nodal lesions, short axis for nodal lesions) for all target lesions will be calculated and reported as the baseline sum diameters. If lymph nodes are to be included in the sum, then only the short axis is added into the sum. The baseline sum diameters will be used as reference to further characterize any objective tumor regression in the measurable dimension of the disease.

Non-target lesions. All other lesions (or sites of disease) including any measurable lesions over and above the 5 target lesions should be identified as **non-target lesions** and should also be recorded at baseline. Measurements of these lesions are not required, but the presence, absence, or in rare cases unequivocal progression of each should be noted throughout follow-up.

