6.3.3 Methods for Evaluation of Measurable Disease

All measurements should be taken and recorded in metric notation using a ruler or calipers. All baseline evaluations should be performed as closely as possible to the beginning of treatment and never more than 4 weeks before the beginning of the treatment.

The same method of assessment and the same technique should be used to characterize each identified and reported lesion at baseline and during follow-up. Imaging-based evaluation is preferred to evaluation by clinical examination unless the lesion(s) being followed cannot be imaged but are assessable by clinical exam.

Clinical lesions: Clinical lesions will only be considered measurable when they are superficial (e.g., skin nodules and palpable lymph nodes) and ≥ 10 mm diameter as assessed using calipers (e.g., skin nodules). In the case of skin lesions, documentation by color photography, including a ruler to estimate the size of the lesion, is recommended.

Chest x-ray: Lesions on chest x-ray are acceptable as measurable lesions when they are clearly defined and surrounded by aerated lung. However, CT is preferable.

Conventional CT and MRI: This guideline has defined measurability of lesions on CT scan based on the assumption that CT slice thickness is 5 mm or less. If CT scans have slice thickness greater than 5 mm, the minimum size for a measurable lesion should be twice the slice thickness. MRI is also acceptable in certain situations (e.g. for body scans).

Use of MRI remains a complex issue. MRI has excellent contrast, spatial, and temporal resolution; however, there are many image acquisition variables involved in MRI, which greatly impact image quality, lesion conspicuity, and measurement. Furthermore, the availability of MRI is variable globally. As with CT, if an MRI is performed, the technical specifications of the scanning sequences used should be optimized for the evaluation of the type and site of disease. Furthermore, as with CT, the modality used at follow-up should be the same as was used at baseline and the lesions should be measured/assessed on the same pulse sequence. It is beyond the scope of the RECIST guidelines to prescribe specific MRI pulse sequence parameters for all scanners, body parts, and diseases. Ideally, the same type of scanner should be used and the image acquisition protocol should be followed as closely as possible to prior scans. Body scans should be performed with breath-hold scanning techniques, if possible.

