10.2 PHASE II EXPANSION COHORTS

10.2.1 Expansion Cohort (Urothelial Carcinoma)

The primary objective of this cohort is to determine the clinical response rate to EP0057 and olaparib in patients with bladder cancer. Data from a single trial of 310 patients with metastatic bladder cancer receiving atezolizumb alone demonstrated an ORR of 15%. To establish at least slightly improved efficacy of this treatment combination compared to single agent atezolizumab, the primary objective would be to determine if using the proposed agents would rule out a 10% response rate and result in a response rate consistent with 25%. As such, this cohort of the trial will be conducted using a Simon optimal two-stage phase II trial design (75) to rule out an unacceptably low PR+CR rate of 10% ($p_0=0.10$) in favor of an improved response rate of 25% ($p_1=0.25$). With alpha=0.10 (probability of accepting a poor treatment=0.15) and beta = 0.20 (probability of rejecting a good treatment=0.20), the first stage will enroll 13 evaluable patients, and if 0 to 1 of the 13 have a clinical response, then no further patients will be accrued in this cohort. If 2 or more of the first 13 patients have a response, then accrual would continue until a total of 34 evaluable patients have been treated. As it may take up to several months to determine if a patient has experienced a response, a temporary pause in the accrual may be necessary to ensure that enrollment to the second stage is warranted. If there are 2 to 5 patients with a response out of 34 patients, this would be an uninterestingly low response rate. If there were 6 or more of 34 (17.6%) who experienced a response, this would be sufficiently interesting to warrant further study in later trials. Under the null hypothesis (10% response rate), the probability of early termination is 62.1%.

It is expected that approximately 1 to 2 patients per month may enroll onto this cohort in the trial. Thus, it is expected that 2 to 3 years may be required to enroll up to 34 evaluable patients. To allow for a small number of inevaluable patients, the accrual ceiling for this cohort will be set at 36 patients. Analysis of correlative studies will be exploratory.

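### Urothelial cohort: a lesion irradiated as recently as two weeks before entry can be a target lesion without later progression at that site, so radiation shrinkage can count toward the primary ORR

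*Combined protocol and SAP*

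**What the plan says.** **Lesion rules (6.3.2).** "Measurable lesions are defined as those that can be accurately measured in at least one dimension", with size thresholds by method. Target lesions are "All measurable lesions up to a maximum of 2 lesions per organ and 5 lesions in total, representative of all involved organs". "Target lesions should be selected on the basis of their size (lesions with the longest diameter"; organ representation and reproducible measurement also count. Prior irradiation is not mentioned.

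**Urothelial entry.** Section 2.1.3.4: "Prior antiangiogenic and radiation therapy are permitted (2-week washout from therapy is required". It sets no condition on the irradiated site. Section 2.1.3.3 asks for progressive disease in connection with prior platinum chemotherapy and/or a checkpoint inhibitor, and does not tie it to an irradiated lesion.

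**SCLC entry.** Section 2.1.2.4: "No previous irradiation to the site of measurable or evaluable disease, unless that site had subsequent evidence of progression".

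**Endpoint and decision.** ORR is the primary endpoint of the urothelial cohort (1.1.1.3, 1.2.2.1). Partial response is a fall of at least 30% from baseline in the target-lesion sum (6.3.4.1). The final rule in 10.2.1 is: "If there were 6 or more of 34 (17.6%) who experienced a response, this would be sufficiently interesting". Section 6.3 cites RECIST 1.1 as the governing guideline. Accrual to the cohort ended with the 08/17/2022 amendment (1.2.18, 2.4.2).

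**The concern.** A lesion that is still shrinking from radiation given shortly before entry tells us little about EP0057 plus olaparib. If it sits in the baseline sum, its later shrinkage counts toward the 30% fall and may be recorded as a response to the drugs. The protocol guards against this in the SCLC cohort, whose primary endpoint is 16-week PFS. It does not do so in the urothelial cohort, where response itself is primary and where two responses in 13 keep the cohort open and six in 34 declare it interesting. There is no control arm to show how much shrinkage would have occurred anyway. At stake is an ORR that is too high and a greater chance of taking an inactive regimen forward.

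**Working it through.** **1. Does another provision close the gap?**

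- Confirmation at 4 weeks or later (6.3, 6.3.4.3) does not, because radiation shrinkage can persist.
- Section 4.1.2 limits on-study palliative radiotherapy to bony metastases, and 6.3.2 classes bone lesions as non-measurable. That deals with radiation during the study, so the gap concerns radiation before entry to nodal or visceral lesions.
- Baseline timing helps in part. Section 2.3.2 says "Screening must be completed within 2 weeks prior to C1D1", which puts the urothelial CT after a 2-week washout. Section 6.3.3 says only "never more than 4 weeks before the beginning of the treatment"; read alone, it would let a scan precede the end of radiation by up to 4 − 2 = 2 weeks.

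**2. Reproduce the design in 10.2.1.** Inputs: p0 = 0.10, p1 = 0.25; 13 patients in stage 1, stop at 0 or 1 response; 34 in total, go at 6 or more.

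- Early termination at p0 = 0.9¹³ + 13 × 0.1 × 0.9¹² = 0.2542 + 0.3672 = 0.621. The plan states 62.1%.
- Go probability = Σ over x ≥ 2 of P(X₁ = x | 13, p) × P(X₂ ≥ 6 − x | 21, p). This gives 0.0957 at p = 0.10 and 0.811 at p = 0.25.

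The design reproduces and meets alpha 0.10 and beta 0.20. (The gloss beside alpha in 10.2.1 reads 0.15; the exact error fits 0.10.)

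**3. Illustrate the effect of misattributed responses.** Let f be the share of patients whose only target lesions were recently irradiated, and r the chance that radiation alone gives such a patient a partial response. Neither is in the documents; both are assumed. With a true ORR of 10%, apparent ORR = 0.10 + 0.90 × f × r.

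| f | r | Apparent ORR | Go probability |
|---|---|---|---|
| 0 | – | 10.0% | 9.6% |
| 5% | 30% | 11.4% | 14.9% |
| 5% | 50% | 12.3% | 19.0% |
| 10% | 30% | 12.7% | 21.3% |
| 10% | 50% | 14.5% | 31.0% |

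**4. One misattributed responder.** Suppose one stage 1 patient responds from radiation and the other patients respond at 10%. Stopping then needs no response among the other 12: 0.9¹² = 28.2%, against 62.1%. The go probability becomes 21.6%, against 9.6%. One such response adds 1/34 = 2.9 percentage points to ORR at full enrolment, and 1/13 = 7.7 points if only 13 patients are evaluable.

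**The case against.** **The guideline is cited.** Response is assessed under RECIST 1.1, and 6.3.2 only restates it. Whether the cited source deals with irradiated lesions cannot be checked from these documents. So a reader might infer that irradiated lesions were in fact used as targets, but the documents do not show that. What stands is that the protocol's own rule lacks the condition for urothelial patients, and that for SCLC the authors wrote it out rather than rely on the citation.

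**The illustration leans high.** It counts only patients whose targets were all irradiated. Targets must represent all involved organs, so an untreated lesion in the sum would dilute the shrinkage. New lesions or non-target progression would make the patient a progressor whatever happened in the irradiated lesion. A scan after the washout may already include early shrinkage. All of this is fair.

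**The cohort closed early.** It was closed for slow accrual and competing studies, and the documents do not say whether 34 patients, or even 13, were reached. The 6-of-34 rule may never be applied. A reported ORR would still carry any bias.

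**A recount can bias the other way.** Once outcomes are known, scoring every patient with only irradiated targets as a non-responder would turn some genuine drug responses into failures. This stands, and it is why ORR should be reported both ways.

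**mCRPC.** A reader might infer the same defect there, since 2.1.6.2 allows entry 3 weeks after radiotherapy. The documents support this only weakly: measurable disease was not required (Précis), response also uses PSA, and 10.2.2 calls the cohort exploratory.

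**Conclusion.** The point holds for the urothelial cohort. As written, the lesion rule and the entry criteria together let radiation shrinkage count toward the primary endpoint, and the SCLC criteria show that the protocol recognises the problem. The direction of any bias is upward. Its size cannot be computed: the number of patients irradiated, the sites and the radiation-only response rate are not given, and the effect could be nil. The rise from 9.6% to 15–31% rests on assumed values (5–10% of patients affected, 30–50% of those reaching partial response), a true ORR of 10% and the full 34-patient design. It shows how sensitive the rule is and does not estimate what happened. A reader might also infer that the two-stage design is miscalculated. It is not: its stated early-termination probability reproduces exactly.

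**What to change.** Apply the 2.1.2.4 condition to urothelial target lesions at analysis:

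1. Before ORR is finalised, and without reference to response status, check every urothelial patient's target lesions against the available radiotherapy history. Flag each irradiated lesion that has no documented progression after the radiation.
2. Report ORR as recorded, and ORR with flagged lesions removed from the target sums. Show patients whose only targets are flagged in two ways: as non-responders and as excluded.
3. Do not call the regimen active if that conclusion depends on responses resting only on flagged lesions.
4. Align the wording of 6.3.2 with 2.1.2.4. This is for consistency only: the two expansion cohorts are closed, phase I is complete and SCLC already has the condition.

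A similar check in mCRPC is optional. The cost is a records check and a small supplementary table, and reported ORR may fall slightly. Neither section 6.1 nor the study calendar specifies recording radiation fields, so the history may be incomplete; where it cannot settle whether a lesion was irradiated, the report should say so.

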6.3.3 Methods for Evaluation of Measurable Disease

All measurements should be taken and recorded in metric notation using a ruler or calipers. All baseline evaluations should be performed as closely as possible to the beginning of treatment and never more than 4 weeks before the beginning of the treatment.

The same method of assessment and the same technique should be used to characterize each identified and reported lesion at baseline and during follow-up. Imaging-based evaluation is preferred to evaluation by clinical examination unless the lesion(s) being followed cannot be imaged but are assessable by clinical exam.

Clinical lesions: Clinical lesions will only be considered measurable when they are superficial (e.g., skin nodules and palpable lymph nodes) and ≥ 10 mm diameter as assessed using calipers (e.g., skin nodules). In the case of skin lesions, documentation by color photography, including a ruler to estimate the size of the lesion, is recommended.

Chest x-ray: Lesions on chest x-ray are acceptable as measurable lesions when they are clearly defined and surrounded by aerated lung. However, CT is preferable.

Conventional CT and MRI: This guideline has defined measurability of lesions on CT scan based on the assumption that CT slice thickness is 5 mm or less. If CT scans have slice thickness greater than 5 mm, the minimum size for a measurable lesion should be twice the slice thickness. MRI is also acceptable in certain situations (e.g. for body scans).

Use of MRI remains a complex issue. MRI has excellent contrast, spatial, and temporal resolution; however, there are many image acquisition variables involved in MRI, which greatly impact image quality, lesion conspicuity, and measurement. Furthermore, the availability of MRI is variable globally. As with CT, if an MRI is performed, the technical specifications of the scanning sequences used should be optimized for the evaluation of the type and site of disease. Furthermore, as with CT, the modality used at follow-up should be the same as was used at baseline and the lesions should be measured/assessed on the same pulse sequence. It is beyond the scope of the RECIST guidelines to prescribe specific MRI pulse sequence parameters for all scanners, body parts, and diseases. Ideally, the same type of scanner should be used and the image acquisition protocol should be followed as closely as possible to prior scans. Body scans should be performed with breath-hold scanning techniques, if possible.

PET-CT: At present, the low dose or attenuation correction CT portion of a combined PET-CT is not always of optimal diagnostic CT quality for use with RECIST measurements. However, if the site can document that the CT performed as part of a PET-CT is of identical diagnostic quality to a diagnostic CT (with IV and oral contrast), then the CT portion of the PET-CT can be used for RECIST measurements and can be used interchangeably with conventional CT in accurately measuring cancer lesions over time. Note, however, that the PET portion of the CT introduces additional data which may bias an investigator if it is not routinely or serially performed.

Ultrasound: Ultrasound is not useful in assessment of lesion size and should not be used as a method of measurement. Ultrasound examinations cannot be reproduced in their entirety for independent review at a later date and, because they are operator dependent, it cannot be guaranteed that the same technique and measurements will be taken from one assessment to the next. If new lesions are identified by ultrasound in the course of the study, confirmation by CT or MRI is advised. If there is concern about radiation exposure at CT, MRI may be used instead of CT in selected instances.

Endoscopy, Laparoscopy: The utilization of these techniques for objective tumor evaluation is not advised. However, such techniques may be useful to confirm complete pathological response when biopsies are obtained or to determine relapse in trials where recurrence following complete response (CR) or surgical resection is an endpoint.

Tumor markers: Tumor markers alone cannot be used to assess response. If markers are initially above the upper normal limit, they must normalize for a patient to be considered in complete clinical response. Specific guidelines for both CA-125 response (in recurrent ovarian cancer) and

PSA response (in recurrent prostate cancer) have been published (62-64). In addition, the Gynecologic Cancer Intergroup has developed CA-125 progression criteria which are to be integrated with objective tumor assessment for use in first-line trials in ovarian cancer (65).

Cytology, Histology: These techniques can be used to differentiate between partial responses (PR) and complete responses (CR) in rare cases (e.g., residual lesions in tumor types, such as germ cell tumors, where known residual benign tumors can remain).

The cytological confirmation of the neoplastic origin of any effusion that appears or worsens during treatment when the measurable tumor has met criteria for response or stable disease is mandatory to differentiate between response or stable disease (an effusion may be a side effect of the treatment) and progressive disease.

FDG-PET: While FDG-PET response assessments need additional study, it is sometimes reasonable to incorporate the use of FDG-PET scanning to complement CT scanning in assessment of progression (particularly possible 'new' disease). New lesions on the basis of FDG-PET imaging can be identified according to the following algorithm:

- a. Negative FDG-PET at baseline, with a positive FDG-PET at follow-up is a sign of PD based on a new lesion.
- b. No FDG-PET at baseline and a positive FDG-PET at follow-up: If the positive FDG-PET at follow-up corresponds to a new site of disease confirmed by CT, this is PD. If the positive FDG-PET at follow-up is not confirmed as a new site of disease on CT, additional follow-up CT scans are needed to determine if there is truly progression occurring at that site (if so, the date of PD will be the date of the initial abnormal FDG-PET scan). If the positive FDG-PET at follow-up corresponds to a pre-existing site of disease on CT that is not progressing on the basis of the anatomic images, this is not PD.
- c. FDG-PET may be used to upgrade a response to a CR in a manner similar to a biopsy in cases where a residual radiographic abnormality is thought to represent fibrosis or scarring. The use of FDG-PET in this circumstance should be prospectively described in the protocol and supported by disease-specific medical literature for the indication. However, it must be acknowledged that both approaches may lead to false positive CR due to limitations of FDG-PET and biopsy resolution/sensitivity.

Note: A 'positive' FDG-PET scan lesion means one which is FDG avid with an uptake greater than twice that of the surrounding tissue on the attenuation corrected image.

